STUDY PROTOCOL

TITLE OF STUDY:

iQuit Mindfully: A Randomized Controlled Trial of Mindfulness-based Smoking Cessation Enhanced with Mobile Technology

PRINCIPAL INVESTIGATOR:

[name] [name]., Assistant Professor
Division of Health Promotion & Behavior, School of Public Health, Georgia State University

SUPPORTED BY:

The National Center for Complementary and Integrative Health K23 AT008442 ("Using Mobile Technology to Understand and Encourage Mindfulness for Smoking Cessation")

CLINICALTRIALS.GOV NCT NUMBER: NCT03029819

DATE OF PROTOCOL DOCUMENT: 12/15/2016

PRÉCIS

Study Title

iQuit Mindfully: A Randomized Controlled Trial of Mindfulness-based Smoking Cessation Enhanced with Mobile Technology

Objectives

The proposed study is a pilot investigation of mindfulness-based smoking cessation incorporating between-session text messaging ("iQuit Mindfully"). This will be the first known study to use text messaging to enhance mindfulness treatment.

Design and Outcomes

Participants will be randomly assigned to one of two groups: Mindfulness-based Addiction Treatment (MBAT) or iQuit Mindfully (MBAT with the addition of between-session text messages). Primary outcomes for this development and feasibility study are: 1) feasibility (e.g., attrition, engagement, participant ratings), 2) determining best practice for implementing and refining the text-messaging intervention (e.g., how many texts per day and at what times of day; which types of messages are most helpful; ways of increasing adherence), and 3) an estimate of effect size (based on smoking cessation in iQuit Mindfully vs. MBAT without text messaging).

Interventions and Duration

All participants will receive in-person group treatment based on the 8-week MBAT protocol (Wetter et al., 2009) in addition to nicotine patch therapy and self-help materials. Participants assigned to iQuit Mindfully will receive additional support via text messaging. Assessments will occur at baseline, at each of the weekly in-person visits, at end of treatment, and at 1-month follow-up.

Sample Size and Population

Participants will include English-speaking adult smokers (ages 18-65). Recruitment will target a racially/ethnically diverse sample of individuals with relatively low income levels. Participants (projected $N = 70$) will be randomly assigned to "iQuit Mindfully" (with text messaging) or MBAT (without text messaging). Approximately 10-15 participants will be enrolled per cohort, resulting in 6 cohorts (3 of each treatment).

1. STUDY OBJECTIVES

Primary outcomes for this development and feasibility study are: 1) feasibility (e.g., attrition, engagement, participant ratings; specific definitions of these outcomes are described in section 9), 2) determining best practice for implementing and refining the text-messaging intervention (e.g., how many texts per day and at what times of day; which types of messages are most helpful; ways of increasing adherence), and 3) an estimate of effect size (based on smoking cessation in iQuit Mindfully vs. MBAT). Effect sizes will be of greater importance than statistical significance, given that this is a feasibility study. Secondary analyses will include: 1) effects of treatment conditions on average number of cigarettes smoked per day; 2) effects of treatment on weekly mindfulness practice; 3) effects of treatment on self-reported levels of mindfulness, affect, self-efficacy, coping, dependence, and withdrawal symptoms; and 4) associations between number of sessions attended, weekly mindfulness practice, and abstinence.

2. BACKGROUND AND RATIONALE

Background and Significance

Tobacco use is the leading cause of preventable morbidity and mortality in the U.S. (CDC, 2008; Mokdad, Marks, Stroup, & Gerberding, 2004; USDHHS, 2010). Although most smokers indicate interest in quitting, only 6% quit each year (CDC, 2011b). Mindfulness-based interventions show promise for improving smoking cessation (Brewer et al., 2011; Davis, Fleming, Bonus, & Baker, 2007). For example, research suggests that participants receiving mindfulness training are over 5 times more likely to be abstinent at 17 weeks post-treatment, compared to standard treatment (Brewer et al., 2011). However, although between-session mindfulness practice is thought to be integral in producing benefits (Grow et al., 2015), participants do not always practice mindfulness in daily life (Vettese, Toneatto, Stea, Nguyen, & Wang, 2009). Fortunately, mobile health technology presents unique opportunities for mindfulness research and intervention. Between-session text messaging might be an effective means to encourage participants to use mindfulness techniques in the moments when they need them most, thus enhancing treatment effectiveness.

Enhancing the effectiveness of smoking cessation treatments is especially critical for underserved populations (i.e., members of racial/ethnic minority groups and individuals with low socioeconomic status [SES]), who often have greater difficulty quitting smoking and experience profound tobacco-related health disparities (CDC, 2011a, 2011b; Fagan, Moolchan, Lawrence, Fernander, & Ponder, 2007; Honjo, Tsutsumi, Kawachi, & Kawakami, 2006). Mobile technology is revolutionizing healthcare and might be used to enhance mindfulness-based interventions for smoking cessation in these populations.

Mindfulness

Mindfulness is defined as purposeful, present-focused attention with an attitude of acceptance and non-judgment (Baer, Smith, Hopkins, Krietemeyer, & Toney, 2006; Kabat-Zinn, 1990, 1994). Mindfulness is linked to improved mood, less anxiety and stress (Baer et al., 2006; Brown & Ryan, 2003; Smith et al., 2011), and lower stress reactivity (Bullis, Boe, Asnaani, & Hofmann, 2013).

Among smokers, mindfulness predicts lower negative affect and perceived stress (Adams et al., 2015; Waters et al., 2009), higher expectancies regarding ability to regulate emotions without smoking (Vidrine et al., 2009), and lower nicotine dependence (Vidrine et al., 2009). Brewer et al. (2011) found that in a diverse sample, mindfulness training for smoking cessation produced over 5 times better abstinence rates than standard treatment (31% vs. 6% at 17-week follow-up). In another diverse sample, Vidrine et al. (2016) found that although mindfulness treatment did not differ from cognitive-behavioral therapy (CBT) or usual care in terms of post-treatment abstinence from smoking,

mindfulness was superior in promoting lapse recovery. Among participants who were not abstinent at end of treatment, those who received mindfulness were more likely to regain abstinence by 1 week post-treatment, and this trend approached significance at 23 weeks. Mindfulness may be effective for preventing lapses from transitioning to full-blown relapses. Another study found that African American smokers with greater mindfulness were more likely to quit and to recover abstinence after an early lapse (Heppner et al., 2016). Tang, Tang, and Posner (2013) found that among current smokers, 2 weeks of mindfulness meditation produced a 60% reduction in smoking compared to a relaxation control.

Mobile Technology to Enhance Mindfulness Intervention Effectiveness. Mindfulness-based treatments (e.g., mindfulness-based stress reduction [MBSR] (Kabat-Zinn, 1990, 1994)) encourage participants to practice mindfulness between sessions, and consistent home practice appears to be a key factor in bringing about therapeutic outcomes (Vettese et al., 2009). However, mastering a new skill in treatment does not necessarily mean that it will translate to real-life situations, and a consistent barrier to treatment success occurs when individuals fail to practice mindfulness in daily life. In a recent trial of mindfulness-based smoking cessation, frequency of between-session mindfulness practice was relatively low (Vidrine et al., 2016). In my clinical experience, patients often realize in hindsight that using a particular strategy would have been helpful, but the strategy did not come to mind in that stressful moment (even with the best of intentions). When participants provide information on emotions, smoking urges, and situational circumstances, tailored in-the-moment strategies can be provided through text messages. By prompting participants to practice mindfulness in their daily lives, text-messaging interventions might increase skill level, self-efficacy, and the likelihood that the skill will become part of daily routines (Heron & Smyth, 2010).

Several researchers have implemented text message-based smoking cessation interventions with success, although none have included mindfulness (Abroms et al., 2012; Borland, Balmford, & Benda, 2013; Free et al., 2011; Obermayer, Riley, Asif, & Jean-Mary, 2004; Riley, Obermayer, & Jean-Mary, 2008; Rodgers et al., 2005). A recent review concluded that mobile phone interventions for smoking cessation nearly doubled the likelihood of quitting up to 6 month follow-up, compared to usual care (Whittaker et al., 2012). Research supports text messaging for promoting several health outcomes, including weight loss and diabetes management (Cole-Lewis & Kershaw, 2010; Fjeldsoe, Marshall, & Miller, 2009; Krishna, Boren, & Balas, 2009). These programs are cost-effective and beneficial across age and racial/ethnic groups (Cole-Lewis & Kershaw, 2010; Guerriero et al., 2012).

Focus on Underserved Populations. Disproportionately high rates of smoking are found in low-SES populations (CDC, 2011a). Compared to other racial/ethnic groups, African Americans tend to have greater difficulty quitting smoking and higher incidence and mortality rates for diseases associated with smoking (CDC, 2011b; Cooper et al., 2000; Fagan et al., 2007; Irvin Vidrine, Reitzel, & Wetter, 2009). The leading causes of death among Latinos (i.e., cancer, cardiovascular disease) are related to smoking (Heron, 2012). The majority of research on mindfulness has focused on higher-SES and Caucasian populations. Although mindfulness shows promise with respect to regulating emotion and promoting smoking cessation in diverse groups (Brewer et al., 2011; Szanton, Wenzel, Connolly, & Piferi, 2011), much work is needed to explore possible benefits and underlying mechanisms in these populations. Text messaging may be particularly effective for targeting low-SES and racial/ethnic minority populations. Latinos and individuals living in poverty are especially likely to have only wireless phones (Blumberg & Luke, 2013). In a Pew Research Center study, mean numbers of texts per day for Caucasians, African Americans, and Latinos were 31.2 (median 10), 70.1 (median 20), and 48.9 (median 20), respectively. Whereas mean number of texts per day among individuals with > college education was 23.8 (median 10), those with < high school education texted 58.7 (median 20) times per day (Smith, 2011). Furthermore, text messaging does not require a Smartphone, making it a highly feasible mode of intervention in low-income populations.

The proposed study is a pilot investigation of mindfulness-based smoking cessation incorporating between-session text messaging (“iQuit Mindfully”). This will be the first known study to use text messaging to enhance mindfulness treatment.

3. STUDY DESIGN

In this randomized clinical trial, participants will be randomly assigned to one of two groups: Mindfulness-based Addiction Treatment (MBAT) or iQuit Mindfully (MBAT with the addition of between-session text messages).

Primary outcomes for this development and feasibility study are: 1) feasibility (e.g., attrition, engagement, participant ratings), 2) determining best practice for implementing and refining the text-messaging intervention (e.g., how many texts per day and at what times of day; which types of messages are most helpful; ways of increasing adherence), and 3) an estimate of effect size (based on smoking cessation in iQuit Mindfully vs. MBAT without text messaging).

Secondary analyses will include: 1) effects of treatment conditions on average number of cigarettes smoked per day; 2) effects of treatment on weekly mindfulness practice; 3) effects of treatment on self-reported levels of mindfulness, affect, self-efficacy, coping, dependence, and withdrawal symptoms; and 4) associations between number of sessions attended, weekly mindfulness practice, and abstinence.

Participants will include English-speaking adult smokers (ages 18-65). Recruitment will target a racially/ethnically diverse sample of individuals with relatively low income levels. Participants (projected $N = 70$) will be randomly assigned to “iQuit Mindfully” (with text messaging) or MBAT (without text messaging; see details of interventions in section 5 below). Approximately 10-15 participants will be enrolled per cohort, resulting in 6 cohorts (3 of each treatment).

The study will take place at Georgia State University in Atlanta, GA. All participants will receive in-person group treatment based on the 8-week MBAT protocol (Wetter et al., 2009) in addition to nicotine patch therapy and self-help materials. Assessments will occur at baseline, at each of the weekly in-person visits, at end of treatment, and at 1-month follow-up.

4. SELECTION AND ENROLLMENT OF PARTICIPANTS

Participants will include English-speaking adult smokers (ages 18-65). Recruitment will target a racially/ethnically diverse sample of individuals with relatively low income levels.

Inclusion Criteria

Inclusion criteria are:

- age 18-65 years
- current smoker with history of ≥ 5 cigarettes/day for past year (and CO ≥ 6 ppm*; participants will not be excluded for use of e-cigarettes)
- motivated to quit within next 30 days
- valid home address in the greater Atlanta area
- functioning telephone number
- own a mobile phone with text messaging capacity
- can speak, read, and write in English
- marginal/adequate health literacy (at least a sixth-grade level as determined by the Rapid Estimate of Adult Literacy in Medicine [REALM]; Davis et al., 1991)

*Expired carbon monoxide (CO) will be used for biochemical confirmation of smoking status because it is a simple and noninvasive method that is commonly used in smoking research. [name] and/or research assistants (who have been trained by [name] on CO testing procedures) will administer CO testing. Participants are asked to take a deep breath in, hold their breath for 15 seconds, and then expire into the disposable mouthpiece on the CO monitor. Although some studies have employed cutoff values of 8-10 parts per million (ppm), a growing body of research suggests that values of 8-10 ppm misclassify a large number of smokers as non-smokers (e.g., Javors et al., 2005; Raiff et al., 2010). A cutoff value of 6 was chosen for the present study because it has been associated with good sensitivity and specificity (Middleton & Morice, 2000) and has been used successfully in recent research (Vidrine et al., 2016).

Exclusion Criteria

Exclusion criteria are:

- contraindication for nicotine patch
- active substance abuse/dependence
- regular use of tobacco products other than cigarettes
- current use of tobacco cessation medications
- pregnancy or lactation
- household member enrolled in the study
- current diagnosis of schizophrenia or bipolar disorder, or use of antipsychotic medications
- Score of ≥ 3 on PHQ-2 depression screening instrument (indicating high likelihood of clinically significant depressive symptoms)

Study Enrollment Procedures

Participants will be recruited through flyers (posted at venues including the GSU campus, local hospitals/community health centers, near MARTA and bus stops, community centers and shelters, etc.) and through print media in local newspapers and on buses and trains. The research team will stimulate recruitment by giving presentations, talking with staff, providing study information, and supplying flyers at local clinics and community organizations in Atlanta, GA. [name] and research staff will also visit primary care practices and health fairs to provide study information and enhance recruitment. Participants will also be recruited through online sources (e.g., Craigslist, listservs) and by word of mouth.

Participants (projected $N = 70$) will be randomly assigned to “iQuit Mindfully” (with text messaging) or MBAT (without text messaging). Approximately 10-15 participants will be enrolled per cohort, resulting in 6 cohorts (3 of each treatment).

Randomization. Randomization will take place at the end of the baseline session, after baseline assessments have been administered. Block randomization will be used to achieve balance in the number of assignments to each treatment group. This form of randomization can be conducted within each stratum (i.e., stratified permuted block design) in efforts to achieve both covariate balance and treatment balance (Hedden, Woolson, & Malcolm, 2006). Thus, in the present study stratified permuted block design will be used, and it will be most important to stratify on variables expected to interact with the text messaging intervention to predict smoking cessation. Given that younger adults typically send and receive more text messages than older adults, age is an important stratification factor. Data from the Pew Research Center indicate that mean number of texts sent/received per day is 87.7 among people aged 18-29; 27 texts/day among people ages 30-49; 11.4 texts/day among those aged 50-64; and 4.7 texts/day among those 65 and older. Thus, stratification will be based on ages 18-49 vs. 50-65 (this cutoff is consistent with the Pew Center data and also lines up with data

from [name] randomized controlled trial of mindfulness-based smoking cessation treatment, in which approximately 50% of participants were 49 or younger.)

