Before in-person assessment of eligibility criteria, participants will review the consent form for in-person screening. Study personnel will offer an opportunity for participants to ask questions and have them answered, the consent form for in-person screening will be signed and dated by the participant and staff member, and a copy of this form will be given to the participants. Then, in order to confirm eligibility, participants will provide a breath sample for assessment of expired carbon monoxide. Health literacy will be assessed with the Rapid Estimate of Adult Literacy in Medicine (REALM; Davis et al., 1991), and for the proposed study participants who have at least a sixth-grade level will be eligible. Individuals who decline or are ineligible will be given self-help materials and referral to other cessation programs. In addition, potential participants will complete the Patient Health Questionnaire-2 (PHQ-2; Kroenke, Spitzer, & Williams, 2003; Lowe, Kroenke, & Grawe, 2005) and answer a question regarding psychotic disorders in order to screen for clinically significant depressive symptoms and psychotic disorders, respectively. Individuals who are not eligible for these reasons will be provided with appropriate mental health referrals in addition to smoking cessation referrals.

Next, the research staff will engage eligible individuals in a discussion of pros and cons of participating, as well as participants' ambivalence about behavior change and research participation (these methods have been suggested to improve retention; Goldberg & Kiernan, 2005).

For eligible individuals who are interested in participating, study personnel will initiate the informed consent process which will include: 1) A thorough review of the Informed Consent Form (ICF), particularly study procedures; 2) Study personnel will offer an opportunity for participants to ask

questions and have them answered; 3) The ICF will be signed and dated by the participant and staff member; and 4) A copy of the ICF will be given to the participants.

Study personnel will explain the text messaging procedures in detail and send a test message to the participant, who will respond and ask any questions. Participants will indicate when they typically wake up and when they typically go to bed. This information will be used so that text messages will only be sent during the hours specified by each individual participant.

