Individuals who would like to participate and express informed consent will then be asked to complete questionnaires. Descriptions of the assessments are provided below:

- The *Telephone Screening* assesses eligibility criteria and demographic characteristics, including age, race, ethnicity, education, employment, and income.
- *Tobacco History* assesses onset of regular smoking, previous quit attempts, abstinence history, smoking rate, and partner smoking status. This includes the *Heaviness of Smoking Index* comprises two items from the *Fagerström Test for Nicotine Dependence* (FTND) (Heatherton, Kozlowski, Frecker, & Fagerstrom, 1991): self-reported average number of cigarettes smoked per day and time to first cigarette upon waking (“time to first cigarette”). The HSI is a strong indicator of nicotine dependence (Kozlowski, Porter, Orleans, Pope, & Heatherton, 1994).
- The *Rapid Estimate of Adult Literacy in Medicine* (REALM)(Davis et al., 1991) is a rapid screening instrument that is used to assess health literacy. It takes 2-3 minutes to administer and score and is highly correlated with comprehensive literacy diagnostic instruments. Individuals are classified as having limited (\leq 6th grade reading level; REALM=0 to 44), marginal (7th- to 8th-grade reading level; REALM=45 to 60), or adequate (\geq 9th grade reading level; REALM=61 to 66) health literacy skills. Participants with scores \leq 44 will be excluded from the proposed study.
- In order to assess for *current psychotic disorders*, participants will be asked, “Do you have a current diagnosis of Schizophrenia or Bipolar Disorder or take anti-psychotic medications such as Haldol or Thorazine?”. Individuals who answer affirmatively will not be eligible but will be provided with appropriate mental health referrals.

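### Does the sixth-grade wording of the literacy criterion, set against a REALM cut-off that starts at seventh grade, change who is enrolled?

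*Combined protocol and SAP*

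**What the plan says.** Three places in the combined protocol and SAP bear on the literacy floor.

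- **Section 4, Inclusion Criteria.** The criterion has a category label and a grade in parentheses: "marginal/adequate health literacy (at least a sixth-grade level". It ties the grade to the REALM: "at least a sixth-grade level as determined by the Rapid Estimate of Adult Literacy in Medicine [REALM".
- **Section 6, In-Person Baseline Visit and Consent Procedure.** Here only the grade is given: "participants who have at least a sixth-grade level will be eligible".
- **Section 6, descriptions of the assessments.** The REALM bands are printed with their grades, the limited and marginal bands as "6th grade reading level; REALM=0 to 44), marginal (7th- to 8th-grade reading level; REALM=45 to 60". The adequate band is ninth grade or above, REALM 61 to 66. The exclusion is then stated as a score: those at or below "44 will be excluded from the proposed study".

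On timing, section 4 says: "Randomization will take place at the end of the baseline session, after baseline assessments have been administered".

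**The concern.** An eligibility criterion should give one answer for each person screened. Read literally, the grade wording admits a sixth-grade reader and the score rule turns the same person away. The grade wording appears twice, once in the formal inclusion list and once in the screening procedure, so it is not a single stray phrase.

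The literacy floor also matters for how the results are read. Recruitment targets people with relatively low incomes, and the component under test is delivered as written text messages. Someone judging to whom the feasibility findings apply needs to know the lowest reading level admitted. If the grade phrase were copied into a report, that level would be stated as one grade too low.

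**Working it through.** This is a check of definitions; no power, error-rate or sample-size formula applies.

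**Inputs, all from section 6 (assessment descriptions) except the last two**

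| Rule | Source | Content |
|---|---|---|
| Limited band | Section 6 | REALM 0 to 44, sixth grade or below |
| Marginal band | Section 6 | REALM 45 to 60, seventh to eighth grade |
| Adequate band | Section 6 | REALM 61 to 66, ninth grade or above |
| Score exclusion | Section 6 | 44 or below is out |
| Category label | Section 4 | marginal or adequate |
| Grade phrase | Sections 4 and 6 | sixth grade or above |

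**Step 1: the score rule.** Removing 0 to 44 from 0 to 66 leaves 45 to 66. The lowest band left is marginal, so the lowest eligible grade is the seventh.

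**Step 2: the category label.** Marginal (45 to 60) together with adequate (61 to 66) is 45 to 66. This is exactly the set in step 1, so the label "marginal/adequate health literacy" and the score exclusion agree.

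**Step 3: the grade phrase.** Its floor is sixth grade. The gap from step 1 is 7 − 6 = 1 grade.

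**Step 4: can the grade phrase be applied separately?** It would need a REALM score at which sixth grade begins. The documents print only the pooled band, "6th grade reading level; REALM=0 to 44", with no division inside it. No score from 0 to 44 can be identified as sixth grade rather than lower.

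**Step 5: apply the rules together.** Anyone scoring 45 or more is at seventh grade or above, so also meets the weaker sixth-grade condition. Anyone scoring 44 or less fails the score exclusion whatever their grade. Meeting both rules is the same as scoring 45 or more.

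**Step 6: does a text-extraction fault explain it?** No. If the symbol before the limited band's grade meant strictly below sixth grade, sixth grade would fall in no band, and the marginal band would still start at seventh grade and 45.

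**Step 7: where else is the REALM used?** It is given at in-person eligibility screening, before randomisation. Section 4 stratifies by age only (18 to 49 against 50 to 65). Neither the analyses in section 9 nor the secondary analyses in section 1 use it.

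**The case for a change.** The strongest case for acting is that the contradiction needs no outside source to see, sits in the formal inclusion list, recurs in the screening procedure, and would cost only a wording change in two places. The baseline-visit text gives the grade and no score, so a staff member working from that paragraph alone could take someone scoring just under 45 to be a sixth-grade reader and let them through. The documents do not state what the sponsor intended: the grade appears twice, while the label and the score support the higher floor.

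Some of this stands. The passages do not match, and no other text reconciles them. A report should describe the sample by the REALM score or the category label, not by the grade phrase.

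The rest carries little weight. The explicit score exclusion is in the same section as the baseline-visit text, and the grade is itself read from the REALM, so staff have to score the instrument to decide. Once they have a score, the printed bands lead to one decision. If someone below 45 were nevertheless admitted, it would happen before allocation and could not favour either arm; the sample would be slightly broader than the score rule allows.

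**Conclusion.** This is a clerical slip in the wording of a criterion whose operative rule is already clear. It amounts to one grade level in a label. The category label and the score exclusion give the same eligible set, REALM 45 to 66, and the grade phrase adds no rule that can be carried out. Aligning the words with the score rule would alter nobody's enrolment under that rule, and no stratum, sample size, analysis or conclusion about the arms.

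The conclusion rests on two assumptions: that staff screen on the REALM score, as section 6 directs, and that the sponsor means the cut-off it printed. If the sponsor did intend to admit sixth-grade readers, the score rule would be the text at odds with that intent, and the printed bands could not supply a replacement score. Nothing in the documents beyond the grade phrase itself points that way. How many people lie at the margin cannot be worked out, since no REALM distribution is given for the target population.

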9. STATISTICAL CONSIDERATIONS AND DATA ANALYSES

Primary outcomes for this development and feasibility study are: 1) feasibility (e.g., attrition, engagement, participant ratings), 2) determining best practice for implementing and refining the text-messaging intervention (e.g., how many texts per day and at what times of day; which types of messages are most helpful; ways of increasing adherence; these variables will be assessed through participant feedback in the individual interview and final program evaluation questionnaire), and 3) an estimate of effect size (based on smoking cessation in iQuit Mindfully vs. MBAT).

Approximately 35% attrition will be deemed acceptable (based on 34% attrition in Vidrine et al.'s (2016) trial of mindfulness-based smoking cessation treatment). Level of engagement will be determined based on: 1) the proportion of texts that participants indicate reading (we expect that at least 75% will read most or all texts, based on Abroms et al.'s (2012) findings); and 2) responses to interactive text messages (we expect that at least 85% of participants will respond to at least one of the interactive text messages or use the CRAVE, STRESS, or SLIP keywords at least once, based on Heminger et al.'s (2016) findings). In terms of participant ratings, we will focus on ratings of helpfulness of the text messages and the extent to which participants would recommend the text messaging program to others (rated on 1-10 scales; the minimum acceptable rating is 6).

Effect sizes will be of greater importance than statistical significance, given that this is a feasibility study. Smoking abstinence will be defined as self-reported complete abstinence for 7 days that is biochemically confirmed with expired carbon monoxide <6ppm. Chi-square tests and t-tests will be used to evaluate group differences.

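### Randomization is stratified by age because age is expected to modify the texting effect, but section 9 never uses the stratum: the pooled comparison stays unbiased, yet it is mildly conservative if age predicts quitting and cannot show that difference

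*Combined protocol and SAP*

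**What the plan says.** Section 4 (Randomization) adopts stratified permuted blocks. It mentions balance, both on the covariate and in arm numbers, as the general purpose of such a design. It then explains how the factor is to be chosen: "it will be most important to stratify on variables expected to interact with the text messaging intervention to predict smoking cessation". Age is picked because of texting habits: "Given that younger adults typically send and receive more text messages than older adults, age is an important stratification factor". The survey means it cites fall from 87.7 texts a day at ages 18-29 to 11.4 at ages 50-64. The outcome is that "stratification will be based on ages 18-49 vs. 50-65". The cut-off is also supported by an earlier mindfulness cessation trial, in which "approximately 50% of participants were 49 or younger".

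Section 9 describes the between-arm analysis in one sentence: "Chi-square tests and t-tests will be used to evaluate group differences". The feasibility measures there (attrition, texts read, replies, ratings) are stated for the whole group. The secondary analyses in sections 1 and 3 concern cigarettes per day, mindfulness practice, questionnaire scores, and associations of attendance and practice with abstinence. None of these, and nothing else in the visible text, mentions an age-adjusted, age-stratified or by-age result.

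**The concern.** The protocol makes a prediction about effect modification, builds it into the allocation, and then plans an analysis that cannot see it. Two things follow.

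First, when allocation is balanced within a factor that predicts the outcome, a test that ignores the factor uses a variance that still contains the between-stratum part, so it tends to reject too rarely.

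Second, the average over two strata says nothing about how they differ. The effect size for abstinence is a primary outcome, and so is learning how to refine the text program. Whether texting suits smokers aged 50-65 bears on both. If results by age are not prespecified, any that appear later will look data-driven.

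**Working it through.** **Inputs from the documents.** Projected N = 70; balanced blocks; two age strata; about half of an earlier trial's participants aged 49 or younger; 35% attrition regarded as acceptable. **Assumptions, because the documents are silent:** 1:1 allocation (35 per arm), an even age split as in the earlier trial, all abstinence rates, two-sided 5%, and independent participants.

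**The plan's own figure.** N = 70 comes with no alpha, power or abstinence rates, so it cannot be derived. It is consistent with 6 cohorts of 10-15 (60-90 people).

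**1. Cell sizes.** 70/2 = 35 per arm; 35 × 0.5 = 17.5 per arm-by-age cell. If 35% are lost and leave the analysis, 17.5 × 0.65 = 11.4.

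**2. What pooling shows.** With equal strata the pooled risk difference is the mean of the two stratum differences. Gains of +20 and 0 points pool to (20 + 0)/2 = +10; +15 and −15 pool to 0. Reply rates of 95% and 75% pool to 85%, the level section 9 expects. These values are illustrative.

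**3. Size of the unstratified test.** With equal strata and rates p1 and p2, the variance the plain test uses per person is the within-stratum variance plus ((p1 − p2)/2)². Under balanced allocation the second term does not contribute to the true variability of the risk difference.
- 15%/35%: 0.1775 + 0.0100 = 0.1875
- 10%/40%: 0.1650 + 0.0225 = 0.1875
- 20%/30%: 0.1850 + 0.0025 = 0.1875

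Simulation under no treatment effect (400,000 replicates, 35 per arm split 18/17 by stratum):

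| Abstinence by stratum | Chi-square size | CMH size, (n−1) variance |
|---|---|---|
| 15% / 35% | about 4.2% | about 4.9% |
| 10% / 40% | about 3.4% | about 4.9% |
| 20% / 30% | about 4.6% | about 4.8-4.9% |

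The 15%/35% entries move by a tenth of a point or two with which stratum holds the 18. In standard-error terms the gain is small. The true SD of the risk difference against the mean unstratified SE is 0.1004 against 0.1014 at 15%/35% (about 1%), and 0.0964 against 0.1014 at 10%/40% (about 5%). At 20%/30% there is no gain (0.1027 against 0.1016).

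**4. What a stratified estimate changes.** The Mantel-Haenszel risk difference weights each stratum by n₁n₀/(n₁ + n₀). With equal arm sizes n in a stratum this is n/2, so the weighted average equals the crude difference. In simulation the two agreed to rounding error. The stratified analysis alters the test and the interval, and does not by itself reveal an age difference.

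**5. What by-stratum results could show.** Take 20% control abstinence, with +20 points in the younger stratum and 0 in the older. The 95% half-widths are:
- Younger: 1.96 × √[(0.40×0.60 + 0.20×0.80)/17.5] = 29.6 points
- Older: 1.96 × √[(0.20×0.80 + 0.20×0.80)/17.5] = 26.5 points
- Difference between strata: 1.96 × √(0.72/17.5) = 39.8 points

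At 11.4 per cell these become 36.8, 32.9 and 49.3. Keeping the +20/0 pattern and varying control abstinence from 10% to 30%, the younger half-width runs from 25.7 to 31.8 and the older from 19.9 to 30.4 (17.5 per cell). In the 20% scenario the power of an interaction test is about 17% (about 13% after attrition), and 80% power would need about 568 people.

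**The case against.** The strongest reply is that stratified blocks achieve balance whatever test follows, that no age objective appears in sections 1, 3 or 9, and that the crude comparison validly estimates the average effect. All of that stands. A reader might infer that ignoring the stratum biases the primary estimate or inflates false positives, but steps 3 and 4 show neither. A reader might also infer that the trial set out to measure an age interaction. The documents give an expectation used to choose a stratification factor, not an objective.

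It can also be said that the conservatism is slight and rests on assumed rates and independent participants. That is correct. Treatment is given in groups. With 70/6 = 11.7 per group and an assumed intraclass correlation of 0.01-0.05, the true SE exceeds the independence-based one by a factor √(1 + 10.7 × ICC), or 1.05 to 1.24. That could equal or outweigh the conservatism, so the net direction of error in this trial is not established.

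Finally, cells this small invite over-reading. Engagement exists only in the texting arm: 13 of 17 older participants replying (76%) has an exact 95% interval of 50% to 93%. The even age split is an earlier trial's figure, and the 85% reply level is an expectation, not a pass mark. So the plan cannot be said to risk passing a criterion that older participants fail.

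What survives is that section 4 justifies its choice of age by expected interaction, and section 9 leaves that expectation unexamined. Since "Effect sizes will be of greater importance than statistical significance, given that this is a feasibility study", descriptive estimates by age fit the study's stated purpose, and wide intervals are no reason to omit them.

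**Conclusion.** The mismatch is real and modest. The planned comparison is unbiased for the average effect. If age predicts quitting and participants are independent, the chi-square is mildly conservative: about 4.2% or 3.4% against a nominal 5% in the two stronger scenarios, and little different from CMH at 20%/30%. The more useful point is that pooled effect size, engagement and ratings cannot show the age difference used to justify the stratification. At N = 70 the by-age output can be descriptive only. This is a minor-to-moderate improvement to the analysis plan, resting on assumed abstinence rates, 35 per arm and an even age split.

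**What to change.** In section 9:

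1. Test abstinence with a CMH test stratified by age 18-49 versus 50-65, using the (n−1) variance, and report the Mantel-Haenszel risk difference or odds ratio with a 95% interval. Replace the t-tests for continuous outcomes with a linear model containing arm and age stratum.
2. Report the abstinence effect size in each age stratum with a 95% interval, and the age-by-arm contrast with its interval. In the texting arm, report engagement and ratings by stratum. Prespecify all of these as descriptive, with no subgroup test or claim.

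The stratum is already recorded at randomization, so the change is to wording and analysis code only. The cost is interpretive: with about 17-18 people per cell, or about 11 after attrition, the intervals are wide and could be over-read. The descriptive label and the intervals must therefore accompany every by-age figure. The precision gained by stratifying is small and should not be offered as the main reason. Neither step deals with clustering by treatment group.
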